4.2.3.4 Vital signs

Height, weight, BMI, Pulse rate, respiratory rate, systolic and diastolic blood pressure, peripheral oxygen saturation and temperature will be listed by patient and summarized for the absolute value at each visit.

Box plots for absolute values and change from baseline by visit may be presented for certain vital signs parameters if warranted after data review.

4.2.3.5 Physical examination

Physical examination findings will be reported as adverse events.

4.2.3.6 Electrocardiogram

ECG details will be listed individually by patient.

The overall ECG evaluations, classified as normal, borderline, abnormal not clinically significant and abnormal clinically significant will be summarized using shift tables summarising the change from baseline to last on-treatment observation, a shift table of baseline evaluation to worst evaluation on-treatment will be produced if sufficient assessments are recorded to allow this.

4.2.3.7 Exposure and compliance

Study treatment exposure data will be listed for each patient.

The total and actual duration of durvalumab monotherapy and combination treatment exposure will be summarized.

Number of patients with at least one delay (and reason for delay), the number of patients with no delay, the number of dosing occasions and the RDI will also be summarized.

4.2.3.8 Other safety data

Other safety data will be listed and/or summarized:

- Tanner stage
- Performance status (Karnofsky or Lansky – the scale appropriate to the patient at the time of screening will be used through the study)

4.2.4 Pharmacokinetic and Immunogenicity analysis

4.2.4.1 Pharmacokinetics - PK parameters

PK data will be summarized and analyzed based on the PK analysis set.

PK concentration data will be listed for each patient and each dosing day, and a summary will be provided for all evaluable patients at each planned time point.

Serum concentrations at each time point will be summarized using the following summary statistics:

- The geometric mean (gmean), calculated as $\exp[\mu]$, where μ is the mean of the data on a logarithmic scale.
- CV, calculated as $100 \sqrt{[\exp(s^2)-1]}$, where s is the STD of the data on a log scale
- Arithmetic mean calculated using untransformed data
- STD calculated using untransformed data
- Minimum
- Median
- Maximum
- Number of observations

The following summary statistics will be presented for C_{\max} ($\mu\text{g/mL}$), C_{\min} ($\mu\text{g/mL}$), time to C_{\max} , and AUC after the first dose, if the data allow

- Gmean, calculated as $\exp[\mu]$, where μ is the mean of the data on a logarithmic scale
- CV, calculated as $100 \sqrt{[\exp(s^2)-1]}$, where s is the STD of the data on a log scale
- Arithmetic mean calculated using untransformed data
- STD calculated using untransformed data
- Minimum
- Median
- Maximum
- Number of observations

The following conventions will be applied to values below the lower limit of quantitation (LLOQ) for summarising PK data:

- If, at a given time point, 50% or less of the blood concentrations are non-quantifiable (NQ), the gmean, CV, geometric standard deviation (geoSD), arithmetic mean and STD are calculated by substituting the limit of quantification (LOQ) for values which are NQ.
- If more than 50%, but not all, of the concentrations are NQ, the gmean, CV, geoSD, arithmetic mean and STD are reported as not calculable (NC)
- If all the concentrations are NQ, the gmean and arithmetic mean are reported as NQ and the CV, geoSD and STD as NC
- The number of values above LLOQ are reported for each time point along with the total number of collected values

Samples below the lower limit of quantification will be treated as zero in predose samples and as missing subsequently in the analyses.

The PK data for after a single-dose and separately will also be displayed graphically. Displays will include serum concentration patient profiles (on the linear and log-scale) versus time and gmean concentration (\pm STD) versus time, stratified by dose.

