CSR	Clinical study report
CT	Computed tomography
CTCAE	Common Terminology Criteria for Adverse Event
CTLA-4	Cytotoxic T-lymphocyte-associated antigen 4
CV	Coefficient of variation
DCR	Disease control rate
DCO	Data cut off
DLT	Dose-limiting toxicity
DoR	Duration of response

Abbreviation or special term	Explanation
DRC	Data Review Committee
ECG	Electrocardiogram
eCRF	electronic case report form
FAS	Full analysis set
GeoSD	Geometric standard deviation
Gmean	Geometric mean
HCV	Hepatitis C virus
HIV	Human immunodeficiency virus
HLT	Higher-level terms
ICs	Immune cells
IHC	Immunohistochemistry
imAE	Immune-mediated adverse event
INRC	International Neuroblastoma Response Criteria
irAE	Immune-related adverse event
irRECIST	Immune-related Response Evaluation Criteria in Solid Tumors
KM	Kaplan-Meier
LD	Longest diameter
LLOQ	Lower limit of quantitation
MedDRA	Medical Dictionary for Regulatory Activities
MR	Minor response
MRI	Magnetic resonance imaging
MTD	Maximum tolerated dose
NA	Not applicable
NB	Neuroblastoma
NC	Not calculable
NCI	National Cancer Institute
NE	Not evaluable
NED	No evidence of disease
NK	Natural killer
NQ	Non-quantifiable
NTL	Non-target lesion
ORR	Objective response rate

Abbreviation or special term	Explanation
OS	Overall survival
OS12/24	Proportion of patients alive at 12 / 24 months from first dose of study treatment
PCR	Polymerase chain reaction
PD	Progression of disease
PD-L1	Programmed cell death ligand 1
PD-L2	Programmed cell death ligand 2
PFS	Progression-free survival
PK	Pharmacokinetics
PR	Partial response
PT	Preferred term
q4w	Every 4 weeks
RDI	Relative dose intensity
RECIST	Response Evaluation Criteria in Solid Tumors
RNA	Ribonucleic acid
RP2D	Recommended Phase II dose
SAE	Serious adverse event
SAP	Statistical Analysis Plan
SARC-1	Osteosarcoma and Ewing sarcoma
SARC-2	Rhabdomyosarcoma, non-rhabdomyosarcoma, and other sarcomas
SARCOMA	Osteosarcoma and Ewing sarcoma; soft-tissue sarcomas: Rhabdomyosarcoma, non-rhabdomyosarcoma, and other sarcomas
SAS	Safety analysis set
SD	Stable disease
SoA	Schedule of activities
SOC	System organ class
STD	Standard deviation
STO	Other solid tumors
TL	Target lesion
TSH	Thyroid stimulating hormone
ULN	Upper limit of normal

AMENDMENT HISTORY

Date	Brief description of change

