Categorical data will be summarized by the number and percentage of patients in each category. Continuous data will be summarized using descriptive statistics, including n, arithmetic mean, STD, median, minimum, and maximum values. Additionally, geometric means and coefficient of variation (CV)% will be reported for PK variables (concentrations and all PK parameters). The geometric mean is calculated as the exponential of the arithmetic mean calculated from data on a log scale. All data will be listed.

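### The planned mean PK figure puts arithmetic SD bars around a geometric mean; the bars should be built from the geometric SD, or the centre changed to the arithmetic mean

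*SAP*

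**What the plan says.** The figures are described at the end of SAP 4.2.4.1. They comprise "serum concentration patient profiles (on the linear and log-scale) versus time and gmean concentration" and then, after a plus/minus sign, "STD) versus time, stratified by dose". The individual profiles are to be drawn on both scales. No axis scale is given for the geometric mean figure.

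The statistics are defined earlier in the same section:

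- The geometric mean is exp(μ), where μ "is the mean of the data on a logarithmic scale".
- The SD appears in both lists of summary statistics as "STD calculated using untransformed data".
- The CV formula uses a log-scale SD and says so: "where s is the STD of the data on a log scale".
- The rules for values below the limit of quantification name "geometric standard deviation (geoSD), arithmetic mean and STD are calculated by substituting" as separate items. The abbreviation list has an entry for "Geometric standard deviation" and another for STD.

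SAP 4.1 says that "geometric means and coefficient of variation (CV)% will be reported for PK variables", so there the geometric mean goes with the CV. Protocol 9.4.3.2 plans individual and mean profiles and does not specify error bars.

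**The concern.** A geometric mean is the back-transformed mean of logged data. Its matching spread is multiplicative: divide and multiply by the geometric SD. An arithmetic SD added to and subtracted from that centre describes neither scale. For right-skewed concentrations the lower bar comes out too long, and the interval no longer contains the share of patients that a reader expects from a one-SD bar. With enough variability the lower limit falls to zero or below.

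What is at stake is how the figure is read. It shows concentration over time by dose in a study that asks whether children reach adult exposure, and the distortion is largest on the low side.

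**Working it through.** The documents state no figure for this point, so there is nothing to reproduce. The check is the size of the mismatch under stated assumptions.

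**Inputs.** The definitions of the geometric mean, STD and CV come from SAP 4.2.4.1. The assumptions are log-normal concentrations at a given time point, a geometric mean scaled to 1, and a between-patient CV varied from 20% to 100% because neither document gives one.

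**Formulas.**

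1. Inverting the SAP's CV formula, CV = √(exp(s²) − 1), gives s = √ln(1 + CV²).
2. The arithmetic SD of a log-normal variable with geometric mean 1 is exp(s²/2) × √(exp(s²) − 1) = CV × √(1 + CV²).
3. The planned bars are 1 − SD to 1 + SD.
4. The matching bars are 1/geoSD to geoSD, with geoSD = exp(s).

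**Worked case, CV 50%.** s = √ln(1.25) = 0.472. SD = 0.5 × √1.25 = 0.559. The planned bars are 0.44 to 1.56. The matching bars are exp(−0.472) = 0.62 to exp(0.472) = 1.60. The planned interval leaves 4.2% of the distribution below it and 17.4% above, so it covers 78.5% (78.4% from these rounded tails). The matching interval covers 68.3%.

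**Range.**

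| Assumed CV | s | SD | gmean ± SD | Coverage | gmean ÷/× geoSD |
|---|---|---|---|---|---|
| 20% | 0.198 | 0.204 | 0.80 to 1.20 | 70.1% | 0.82 to 1.22 |
| 30% | 0.294 | 0.313 | 0.69 to 1.31 | 72.3% | 0.75 to 1.34 |
| 50% | 0.472 | 0.559 | 0.44 to 1.56 | 78.5% | 0.62 to 1.60 |
| 70% | 0.631 | 0.854 | 0.15 to 1.85 | 83.5% | 0.53 to 1.88 |
| 78.6% | 0.694 | 1.000 | 0.00 to 2.00 | 84.1% | 0.50 to 2.00 |
| 100% | 0.833 | 1.414 | −0.41 to 2.41 | 85.5% | 0.43 to 2.30 |

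The last column is always positive and covers 68.3% at every CV.

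**Where the lower bar reaches zero.** Setting CV × √(1 + CV²) = 1 gives CV² = (√5 − 1)/2 = 0.618, so CV = 78.6%.

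Up to about 30% CV the two kinds of bar are close. At 50% the upper limits still nearly agree (1.56 and 1.60), and the difference lies in the lower limit.

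**The case against.** The strongest reply is that the STD in the figure description is loose shorthand for the geometric SD. The quantification-limit rules cover geoSD although neither list of summary statistics includes it, which could mean that it was intended for an output such as this one. Protocol section 9 also refers to mock output shells, which may settle the layout and are not available here. That leaves open what will finally be drawn. It does not rescue the text: the SAP abbreviates the two statistics separately and labels a log-scale SD as such when it means one. A programmer who follows the definitions would draw arithmetic bars, so the wording needs correcting on either reading.

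The reply that the effect may be small also has force. No CV is given, and at 20% to 30% few readers would notice. A negative lower limit needs a CV of about 79% or more, and the documents do not establish that level.

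Three stronger readings are tempting and are not supported:

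- **That the bars will fail on a log axis.** The mention of two scales belongs to the individual profiles, which carry no bars. A limit at or below zero could not be drawn if a log axis were used, but the axis of this figure is not stated.
- **That exposure or dose decisions are affected.** Protocol 4.1.1 and 4.3.1.1 judge exposure on AUC over Days 0 to 28, through the lower 80% confidence limit against 50% of adult exposure, and on 5 of 6 patients at a dose level. The bars do not enter.
- **That the SAP already tabulates geoSD.** It is named only in the quantification-limit rules and the abbreviation list.

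Nor does a reader depend on the bars. The tables give the geometric mean with CV, the arithmetic mean with STD, and the minimum, median and maximum, and individual data are listed and plotted.

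**Conclusion.** The point holds as a minor error of specification. By the SAP's own definitions, the figure pairs a log-scale centre with a linear-scale spread, and that is wrong on either axis. Its visible size depends on a CV that the documents do not give: slight at 20% to 30%, a clearly overlong lower bar at 50% (0.44 against 0.62, coverage 78.5% against 68.3%), and an impossible lower limit from about 79%. These numbers rest on the log-normal assumption and are population values; a sample of about six patients per dose level and arm will scatter around them. The consequence stops at a descriptive figure. The tables are coherent, and no test, exposure criterion or dose decision is touched.

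**What to change.** In SAP 4.2.4.1, change the description of the mean figure in one of two ways:

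- plot the geometric mean with limits gmean/geoSD and gmean × geoSD, and add geoSD to the list of concentration summary statistics, defined as exp(s) with the s already used in the CV formula; or
- plot the arithmetic mean ± STD, both of which are already listed.

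In either case, state whether the axis is linear or logarithmic, and check the mock shell for this figure against the revised text. The cost is a phrase in the SAP, one added line if geoSD is tabulated, and a plotting option. No new data or analysis is needed.

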4.2.4.2 Pharmacokinetic relationships

If the data are suitable, the relationship between PK exposure and efficacy/safety parameters may be investigated.

A population PK model will be developed using a non-linear mixed-effects modeling approach. The impact of physiologically-relevant patient characteristics (covariates) and disease on PK will be evaluated. The relationship between the PK exposure and the effect on safety and efficacy endpoints will be evaluated if the data allow. The results of such an analysis will be reported in a separate report. The PK, demographic, safety, and efficacy data collected in this study may also be combined with similar data from other studies and explored using population PK and/or PK-pharmacodynamic methods.

4.2.4.3 Immunogenicity - ADAs

A summary will be provided of number and percentage of patients who develop detectable ADAs. The immunogenicity titer and neutralizing ADA data will be listed for samples confirmed positive for the presence of anti-durvalumab and anti-tremelimumab antibodies.

The summaries will consider durvalumab and tremelimumab evaluability of ADA samples separately. For instance, summaries considering ADA+ to durvalumab and tremelimumab will need to first consider if a patient was both evaluable to durvalumab and evaluable to tremelimumab. Subsequently, if summarizing for ADA+ to durvalumab only, we only consider if a patient was evaluable to durvalumab.

The effect of immunogenicity as well as the effect of its neutralizing properties on PK, efficacy, and safety will be evaluated, if the data allow. A detailed plan will be written by the AstraZeneca Clinical Pharmacology group or designee.

4.2.5 Demographic, patient disposition and baseline characteristics data

The following will be summarized for all patients in the FAS.

Disposition of patients

A summary will be provided for the number of patients enrolled, who received treatment, who completed the study, and who terminated prematurely. Reasons for premature termination will be summarized.

The number of patients in each analysis set, by country and centre will also be summarized.

Demographic data

Descriptive statistics will be presented for age, height, weight and BMI. In addition, frequencies and percentage of patients will be tabulated for the categorical variables age group (0-<6, 6-<12, 12-<18), sex, race and ethnic group.

Other baseline data

Other demographic and baseline data will be listed and/or summarized:

- Medical and surgical history
- Nicotine use categorized (never, current, former)
- Extent of disease at baseline
- Pregnancy information
- Important protocol deviations (both overall, and separate summaries for those related and unrelated to the Coronavirus Disease 2019 (COVID-19) pandemic)
- COVID-19 study disruptions (number and percentage of patients with the following: visits impacted, study drug impacted and concomitant medications not started)
- Inclusion in analysis populations.

Any COVID-19 related summaries will only be produced if there are a minimum of 5 patients with data to present.

4.2.6 Concomitant and other treatment

All medications will be coded using the latest AstraZeneca Drug Dictionary at the time of database lock.

Prior medication is defined as medication with a stop date before the date of the first dose of study treatment

A medication will be regarded as concomitant if the start date is on or after the date of first dose, or if it started prior to the date of first dose and was ongoing after the date of first dose. Separate tables will be presented according to whether the medication is allowed or disallowed. Disallowed medications are detailed in section 6.4 of the CSP and will be identified by the physician throughout the study and merged into the reporting database by IQVIA programming.

Start and stop dates for all concomitant medications are collected on the eCRF. However, in case of missing or partial information in these dates, the following rules will be used:

If start date is missing or partial:

- if month is missing, use January (01)
- if day is missing, use the 1st (01)
- if year is missing, use year of the consent date
- if entire date is missing, use consent date

If stop date is missing, partial or “continuing:”

- if month is missing, use December (12)
- if day is missing, use the last day of the month under consideration
- if year or the entire date is missing or if “continuing”, set to missing.

A patient is only counted once if receiving the medication more than once.

4.2.7 Biomarker data

4.2.7.1 Antibody titer measurements before and after routine immunization

Vaccine antibody titer data will be listed by patient.

4.2.7.2

CCI

will be listed by patient.

CCI

will be reported in the CSR. Summaries and analyses for exploratory biomarkers will be documented in a separate analysis plan and will be reported outside the CSR in a separate report.

Based on availability of data, additional exploratory biomarker analyses may be performed.

5 INTERIM ANALYSES

No formal interim analysis for efficacy is planned for this study. However, in dose-expansion phase, ORR will be evaluated on an ongoing basis for the first 11 evaluable patients (SARCOMA cohort) to complete Stage 1 of the Simon 2-Stage optimal design (see Section 4.1.4 of the CSP). The methodology described in this SAP for the derivation of visit responses and efficacy variables will also be used for the DRC analyses. Further information around the analysis and outputs required to facilitate this will be described in the DRC charter.

6 CHANGES OF ANALYSIS FROM PROTOCOL

As there is no current plan to incorporate irRECIST, this has not been referenced in the SAP.

The definition of the evaluable for response analysis set has been updated to align with the definition in the DRC charter.

An additional sensitivity analysis of ORR using unconfirmed responses has been added.

Clarification has been added that the mid-P methodology is applicable only if the cohorts are expanded.

Visit windowing of safety domains will be considered up to end of treatment, rather than up to progression as mentioned in the protocol.

An additional efficacy listing detailing dose-finding cohort overall RECIST response per investigator assessment has been added.

